9.0 Study Withdrawal/Discontinuation

The study investigators or Vanderbilt University Medical Center may withdraw subjects from this study at any time after they have provided informed consent, but before study completion. Study withdrawal may occur for several reasons including but not limited to: non-compliance with the protocol, concern for patient safety, the availability of new information that may affect continued participation, or if the study is stopped. Subjects are free to withdraw from this study at any time. We will cease to collect study information at the time of withdrawal of consent, but data already collected will be retained. Withdrawal of consent or refusal to participate will not prejudice subject health care.

10.0 Statistical Considerations

In this proposal, we will be testing the general hypothesis that nine weeks of treatment with the sympathetic blocker, moxonidine, will improve insulin sensitivity (Specific aim 1), microvascular blood flow (Specific aim 2), and inflammation (Specific aim 3), in obese hypertensive human subjects. We will be comparing the changes before and after treatment with the central sympathetic inhibitor moxonidine (MOX), versus the changes produced with treatment with the calcium channel blocker amlodipine (AML), an antihypertensive medication considered to have neutral metabolic and anti-inflammatory effects. Our main scientific goal is to demonstrate the efficacy of MOX in a superiority trial, and for that reason the study is powered to perform the main statistical analysis between the MOX and AML arms. The clinical comparison between the two responses, not previously done, will provide important new information. Nonetheless, as a secondary analysis, the differences in primary outcomes between the treatment and baseline study days will be compared across the two study arms using a linear regression model. Given the fact that the degree of obesity, baseline sympathetic activity and blood pressure may affect EGP these variables as well as gender and age will be included as covariates in the model to take into account potential confounding effects. We make no a priori assumptions about the outcome of these studies. Any result, therefore will provide important new information.

a) Specific Aim 1a - The null hypothesis is that there will be no changes in the insulin-mediated suppression of endogenous glucose production in response to sympathetic blockade with MOX. We will evaluate this hypothesis at Visit 9 (post treatment) by measuring EGP at baseline (EGPBsI) and during the last 30 minutes of a hyperinsulinemic euglycemic clamp (EGPClamp) in a double-blind randomized trial (protocol shown in figure 6). For each study arm, the primary endpoint will be DEGP = (EGPBsI – EGPClamp) the difference in the change of insulin-mediated suppression of basal EGP between the pre and post treatment visit. The primary analysis will be performed between the moxonidine and amlodipine arms, at Visit 9 using Welch's unequal-variance an unpaired t-test to test whether the primary end point will be equal in these two treatment groups. Note that although we are collecting multiple measures over time, this endpoint is based on a single visit and a scalar response feature ΔEGP. Hence, a fixed effects analysis is appropriate for this aim. Appropriate non-parametric analysis methods will also be used if data are not normally distributed. Since the degree

of obesity, baseline sympathetic activity, blood pressure, age and gender may affect EGP, these variables could confound the effect of treatment on the change in EGP. For this reason, in a secondary linear regression analysis we will compare DEGP in the moxonidine and amlodipine arms adjusted for these variables. We will also assess the effects of treatment on EGP over time by conducting a repeated-measures GEE regression analysis of EGP against treatment and these confounding variables at baseline and the 9 subsequent visit times. These analyses will use a normal random component and the identity link function. Spaghetti graphs and residual analyses will be used to assess the model fit. Restricted cubic splines will be used if needed to account for non-linear effects of time on treatment response (33).

Sample size calculation. Power calculations are based on previous studies comparing the suppression of EGP between subjects with impaired fasting glucose and normal fasting glucose (34). In this study among obese subjects with impaired fasting glucose (N=30), the mean and the standard error of mean (SEM) for EGP at baseline was 15.2 \pm 0.2 μ mol×min-1 \times kg-1, and during the clamp, EGP was $10.2\pm0.7~\mu\text{mol}\times\text{min-1}~\times~\text{kg1}$. Hence, the standard deviation (SD) of EGP at baseline and during clamp was $0.2\sqrt{30} = 1.1$ and $0.7\sqrt{30} = 3.8$, respectively. We will power our study to detect a difference in inhibition of 3 µmol×min-1 ×kq-1. Making the conservative assumption that clamped and baseline EGP values are independent, we estimate the SD of this difference to be *(1.1, +3.8) = 4.0. With this SD, 29 subjects per group would provide 80% power to detect a mean difference in the inhibitions of 3 μ mol \times min-1 \times kg-1 with the type I error of a = 0.05. Assuming a drop-out rate of 20%, which includes the subjects that will be enrolled based on HOMA but later shown not to have insulin resistance during the clamps (see Section C.2), we will need to enroll 36 subjects in each study arm. This sample size will also be used in Aims 1b, 2 and 3 even though smaller sample sizes would suffice for these aims.

Specific Aim 1b - The null hypothesis is that chronic sympathetic blockade will not improve whole body insulin sensitivity. We will measure insulin sensitivity as the glucose infusion rate, corrected by body weight (MBW) needed to maintain euglycemia during the last 30 minutes of a hyperinsulinemic euglycemic clamp. The same three groups of subjects will be studied twice, at the beginning (BSL) and the end of 9 weeks of treatment with either the sympathetic blocker moxonidine (MOX) or the calcium channel blocker amlodipine (AML). The null hypothesis is that we will not see any difference in the change in body-weight-corrected insulin sensitivity with MOX as compared with AML. The primary analysis will assess changes in MBW (MBW_clamp – MBW_bsl) between patients receiving MOX and will use a t-test similar to that described for Aim 1a.

Sample size calculation. We estimated the sample size based on previous studies (17) using a similar design to the present study, which found a 21% improvement of insulin sensitivity with moxonidine. From our previous studies, we expect obese insulin resistant hypertensive subjects to have a MBW of 3.1 ± 0.99 mg/kg/min (17). An increase of 21% in the moxonidine arm will translate as a MBWMOX of 3.75 mg/kg/min (a difference of 0.65 mg/kg/min), after 9 weeks of treatment. Assuming that a SD of the difference of 0.75

mg/kg/min, a sample size of of 27 subjects per group will provide 88% power to detect this difference with a = 0.05.

Specific Aim 2 - The null hypothesis is that insulin will not produce any different changes in microvascular blood volume (MBV) using contrast enhance ultrasonography (CEU) in response to nine weeks of treatment with moxonidine as compared to amlodipine. We will measure MBV at baseline (MBVbsl), during the last 30 minutes of the lower insulin dose (15 mU/m2 /min) portion of the hyperinsulinemic euglycemic clamp (MBVegp), and during the last 30 minutes of the higher insulin dose (60 mU/m2/min) portion of the clamp (MBVclamp) on two different occasions (double blind, randomized, protocol shown in figure 6). Subjects will be randomized to treatment with moxonidine (MOX) or amlodipine (AML). The primary endpoint would be the average difference in the change in MBV (MBVclamp-MBVbsl) between the MOX and AML arms. The primary analysis will be conducted between the moxonidine and amlodipine arms using a t-test as described in Aim 1a.

Sample size calculation. We estimated the sample size based on our preliminary results (Figure 8) and previous studies in obese human subjects (35). In our study, on the SAL day, we expect to see a blunted increase in MBV only due to insulin among obese subjects (from 20.4 ± 3.6 to 18.8 ± 3.8 , as in the paper by Haenni and Lithell (17)). We believe that an increase of 3.5 arbitrary intensity units (AIU) of MVB (half of the what was seen in healthy subjects) during MOX treatment would be a clinically significant difference. Healthy subjects showed an increase from 18.7 ± 3.3 to 25.0 ± 4.1 in the same paper, and we have observed similar results (see figure 8). With a SD of 3.2 AIU, a sample size of 27 subjects per group would provide 97% power to detect a difference of 3.5 AIU with a = 0.05.

Specific Aim 3 - The null hypothesis is that chronic sympathetic blockade will not improve inflammation in obese hypertensive subjects. We will measure the percent of circulating T cells that express both CD4 and CD45RO (CD4+ /CD45RO+), at baseline and after nine weeks of treatment with each of the study drugs as in the previous specific aims. Obese hypertensive subjects will be studied twice, at the beginning (BSL) and the end of 9 weeks of treatment with either the sympathetic blocker moxonidine (MOX) and the calcium channel blocker amlodipine (AML). The primary outcome variable will be the change from baseline in the CD8+ /CD45RO+ percentage of circulating T cells. The null hypothesis will be that there is no difference in this outcome in patients treated with moxonidine compared to patients treated with amlodipine. The primary analysis will be to conduct an unpaired t-test on the primary outcome that is similar to that described for Aim 1.a. Secondary analyses to account for a possible skewed distribution of the primary outcome, to adjust for potential confounding variables will also be performed in a fashion that is similar to the analyses for Aim 1.a.

Sample size calculation. We estimated the sample size based on previous studies ((36), figure 9) that have found an increased percentage of CD4+

/CD45RO+ circulation T cells in hypertensive human subjects. They found that hypertensive subjects have 20% more circulating T cells expressing both CD4 and CD45RO as compared to healthy controls. We expect to see a reduction of at least 15 ± 5 percent after 9 weeks of treatment with moxonidine. A decrease of 15% in the moxonidine arm will translate as 45% of CD4+ /CD45RO+ (from 60% at baseline), after 9 weeks of MOX treatment. Assuming that a SD of the difference is 15%, a sample size of 27 subjects per arm would provide 95% power to detect a difference of this magnitude with a=0.05.

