6.0 Study Procedures / Study timeline

As explained before, we propose a double-blind, randomized, 9-week, parallel group study. The clinical trial will consist of 9 visits.

Visit 1 (Screening and clinical characterization): We will enroll obese hypertensive subjects off medications. Antihypertensives and medications that can affect autonomic function will be stopped at least for 5 half-lives (~2-3 weeks). They will be asked to monitor their blood pressure at home and will be provided with blood pressure monitors if necessary. Patients with pre-

hypertension are included if they have insulin resistance and sympathetic activation. Stage II hypertension is excluded because of the likelihood that more than one antihypertensive is needed to control BP.

[figure not shown]
Visit 2 and 3 (Baseline measurements): After 3 weeks off medications (or at least 5 half-lives), if the patients still meet the inclusion/exclusion criteria, we will perform the following baseline measurements the day before performing the first hyperinsulinemic-euglycemic clamp:

- Sympathetic activity (MSNA) (visit 2 only)
 - We may perform some autonomic nervous system function tests during MSNA such as Valsalva maneuvers
- Heart rate
- Blood pressure (supine and 1, 3, 5, 15, 30 minutes standing)
- Blood samples collected in supine position and after 30 minutes of standing for catecholamines, renin activity, angiotensin II and aldosterone levels) (visit 2 only)
- Blood for FAC analysis of immune cells (visit 2 only)
- Flow mediated dilation and 24-hr blood pressure (visit 2 only)
- FAC analysis of harvested endothelial cells (visit 2 only)
- Non-invasive determination of arterial stiffness using tonometric (Sphygmocor) method (visit 2 only)
- Hyperinsulinemic clamp (visit 3 only)
- Body impedance (visit 2 or 3)
- Blood volume measurement (visit 2 only)
- DEXA scan (visit 2 only)

Visit 4-7 (Randomization): Randomization, blood pressure adjustments and monitoring will be held from visit 4 to visit 7. Patients will be randomized with a permuted block double-blinded scheme. Moxonidine and amlodipine will be started at 0.2mg bid and 5mg, respectively. Blood pressure will be measured using the Sprint protocol with home monitors provided by us, and at weekly visits. A blinded study physician will increase medication dose once if needed. The dose titration period can be extended if necessary, to reach a stable BP.

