Visit 8-9: We will repeat the baseline measurements mentioned above after 9 weeks of treatment during these visits. Hyperinsulinemic-euglycemic clamp will be performed in visit 9 (treatment). No DEXA scan will be performed at visit 8.

Study procedures during the hyperinsulinemic-euglycemic clamps:

- 1. We will draw a blood sample to measure baseline levels of [6,6-2H2]-dideuterated glucose. We will then start the continuous infusion of [6,6-2H2]-dideuterated glucose. After at least 90 minutes, we will do baseline measurements of HP and BP. We will take blood samples every 15 minutes for 30 minutes (3 total) to measure plasma glucose, insulin, glucagon, C-peptide, and [6,6-2H2]-dideuterated glucose.
- 2. We will then perform a two-hour glucose clamp. In ancillary studies ([name], unpublished) new found that an autonomic blockade enhances insulin suppression of EGP, we decided to use the lower dose of 15 mU/m²/min insulin produced a >50% suppression of EGP (Bock et al. 2007). Plasma glucose will be monitored every 5 minutes and euglycemia (90-100 mg/dl) will be maintained with variable infusion of 20% glucose. Potassium chloride 10 mmol/hr will be infused to prevent hypokalemia.
- 3. Once the glucose clamp is started, the glucose tracer infusion will be gradually reduced to 1.0 mg/m2 (half the starting dose), to account for the expected decrease in hepatic glucose output. To minimize changes in glucose isotopic enrichment, tracer will be added to the 20% Dextrose solution. We will alter tracer delivery commensurate with changes in glucose flux to maintain a constant plasma specific activity of glucose, as done previously (28-31).
- 4. Within the last 30 minutes after achieving stable glucose levels, samples will be drawn for every 15 minutes for 30 minutes (3 total) to measure glucose and [6,6- 2 H2]-glucose levels. At the third blood draw, we will also obtain samples for insulin, glucagon, C-peptide, catecholamines, and free fatty acids. In particular, glucagon and free fatty acids regulate EGP, but we have previously shown that their suppression during hyperinsulinemia is not altered by sympathetic withdrawal (32).

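### The Aim 1a primary endpoint is defined both as a pre-to-post change and as a Visit 9 value; the 80% power belongs to the Visit 9 version, and the Visit 3 value is not a covariate in any model

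*Combined protocol and SAP*

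**What the plan says.** All of this is in section 10.0 of the combined protocol and SAP unless stated otherwise.

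- **Definition of the endpoint (Specific Aim 1a).** The formula is basal EGP minus EGP in the last 30 minutes of the clamp, both from the same clamp day. The sentence that contains it continues with "the difference in the change of insulin-mediated suppression of basal EGP between the pre and post treatment visit".
- **Test (Specific Aim 1a).** A Welch t-test compares moxonidine with amlodipine at Visit 9. A note adds that "this endpoint is based on a single visit and a scalar response feature".
- **General text at the start of section 10.0.** It opens with "We will be comparing the changes before and after treatment with the central sympathetic inhibitor moxonidine" against the changes on amlodipine, but later states that "as a secondary analysis, the differences in primary outcomes between the treatment and baseline study days will be compared across the two study arms".
- **Power.** Basal and clamped SDs from a published clamp study are combined: "Making the conservative assumption that clamped and baseline EGP values are independent, we estimate the SD of this difference to be" 4.0. No between-visit correlation appears.
- **Covariates.** The secondary regression is justified because the degree "of obesity, baseline sympathetic activity, blood pressure, age and gender may affect EGP, these variables could confound the effect of treatment". The general text lists the same five variables. Neither list contains EGP suppression before treatment.
- **Data collected (section 6.0).** The baseline list has "Hyperinsulinemic clamp (visit 3 only"), and for the end of treatment "Hyperinsulinemic-euglycemic clamp will be performed in visit 9 (treatment"). The quantity is therefore measured on both days.

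**The concern.** A quantity based on one visit cannot also be a difference between two visits. An analyst could defend either test as the prespecified primary: the Visit 9 comparison from the formula and the note, or the change score from the sentence that defines the endpoint and from the opening of section 10.0.

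This endpoint sized the trial. Its sample size is carried over to Aims 1b, 2 and 3, whose t-tests are modelled on it. Three things are at stake: which result is the primary one, whether the stated 80% applies to it, and whether the Visit 3 clamp is used well. The Visit 9 test ignores the Visit 3 value. The change score only subtracts it, with a fixed weight of one.

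**Working it through.** **Inputs.** From the Aim 1a sample size paragraph: SEMs 0.2 and 0.7 with N = 30, difference 3 µmol/min/kg, SD 4.0, 29 per arm, alpha 0.05. Two-sided testing is inferred, because a one-sided test would need only 22 per arm. Assumed, because the documents do not give them: equal SD at Visits 3 and 9, and correlation r between the two suppression values, taken as 0, 0.3, 0.5 and 0.7.

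**Step 1: reproduce the plan's figure.** The SDs are 0.2√30 = 1.10 and 0.7√30 = 3.83. Combined as independent, √(1.10² + 3.83²) = 3.99, stated as 4.0. The noncentrality is 3 / (4.0·√(2/29)) = 2.86 on 56 degrees of freedom, which gives power of 80.1%. The plan's figure is correct for a comparison of one clamp per patient, that is, Visit 9.

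**Step 2: the change score.** SD = 4.0·√(2(1 − r)).

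**Step 3: Visit 9 adjusted for Visit 3.** Residual SD = 4.0·√(1 − r²), with 55 degrees of freedom.

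| r (assumed) | Visit 9 test, power | Change SD | Change, power | Change, n per arm for 80% | Adjusted SD | Adjusted, power |
|---|---|---|---|---|---|---|
| 0 | 80% | 5.66 | 51% | 57 | 4.00 | 80% |
| 0.3 | 80% | 4.73 | 66% | 41 | 3.82 | 84% |
| 0.5 | 80% | 4.00 | 80% | 29 | 3.46 | 90% |
| 0.7 | 80% | 3.10 | 95% | 18 | 2.86 | 98% |

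The change score reaches 80% at r = 0.50.

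**Step 4: how often the two readings disagree.** Simulation of normal data, 29 per arm, 100,000 trials per setting, two-sided 0.05:

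| r (assumed) | Opposite verdicts at difference 3 | Either test significant at difference 0 |
|---|---|---|
| 0 | 33% | 8.4% |
| 0.3 | 27% | 8.9% |
| 0.5 | 23% | 9.1% |
| 0.7 | 20% | 9.2% |

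**Step 5: the adjusted model with robust standard errors (HC3).** In 20,000 simulated trials per setting, power was 78%, 81%, 88% and 97%. Type I error was 4.4–4.6%.

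**The case against.** The strongest reply is that the primary test can largely be recovered. The formula, the two references to Visit 9, the single-visit note, the one-clamp SD and the demotion of the between-day difference to secondary all point to Visit 9. One descriptive clause is out of line. This is true of the balance of the text. But the clause sits in the sentence that defines the endpoint, and the opening of section 10.0 supports it.

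Other points, and what stands of each:

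- **Both contrasts estimate the same treatment effect under randomisation.** This stands. They differ in precision and can differ in verdict in one trial, which is why one must be named.
- **The plan has no rule that lets either test count.** This stands. The 8–9% is the cost of leaving the choice open, not a property of a stated procedure.
- **The threshold of 0.50 takes SD 4.0 as exact, while the plan calls its independence assumption conservative.** This stands. If basal and clamped EGP correlate at 0.3 within a clamp (assumed), the SD is √(1.20 + 14.70 − 2·0.3·1.10·3.83) = 3.66, and the change score reaches 80% at r of about 0.40. At 0.5 the SD is 3.42 and the threshold is about 0.31. The power of the change score still depends on an r that is not given.
- **The Visit 3 clamp is not unused, and the unadjusted test is valid.** Both are correct. Visit 3 data enter the secondary between-day comparison and the repeated-measures model as outcomes. Leaving them out as a covariate loses efficiency; it does not cause bias.
- **Correcting the clause alone would be enough.** It would remove the contradiction. It would also leave a measured baseline of the same quantity out of the primary test.

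**Conclusion.** The concern holds. The Aim 1a primary endpoint has two definitions that lead to different tests, and the stated 80% was derived for the Visit 9 test only. The sample size arithmetic itself is right.

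It cannot be said that the change score is underpowered, only that its power runs from 51% to 95% for r from 0 to 0.7. The disagreement rate of 20–33% rests on the same assumed range, on normal data and on equal SDs at the two visits. The contradiction in the text and the missing covariate rest on no assumption. Reconciling the definition is essential. Adjusting for Visit 3 is the better of the ways to do it, because it keeps the Visit 9 comparison for which the trial was sized and uses both clamps.

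**What to change.** 1. State one primary analysis for Aim 1a: a linear model of Visit 9 EGP suppression (basal minus clamped) on treatment arm and the Visit 3 value of the same quantity, with heteroscedasticity-robust standard errors.
2. Replace the pre-and-post wording in the endpoint definition so that it matches, and align the opening of section 10.0.
3. Keep the Welch test at Visit 9 as a sensitivity analysis, and say whether the non-parametric provision attaches to it.
4. Add the Visit 3 value to the secondary covariate model.
5. State that 29 per arm, SD 4.0 and 80% were derived for the Visit 9 comparison.
6. For clarity, say that the clamped EGP comes from the low-dose insulin step, as sections 2.0 and 6.0 already indicate.

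**Cost.** The change is to the text of the analysis plan, made before unblinding, with no new visits, samples or patients. It does replace the named primary test, so it should be recorded as an amendment. One degree of freedom is spent. In the worst case, r = 0, power is 80% by formula. In simulation it is 79% with model-based and 78% with robust standard errors.

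### The secondary repeated-measures GEE for Aim 1a cannot be fitted as written, and the timing of its blood pressure covariate is left open

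*Combined protocol and SAP*

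**What the plan says.** **Visits (Section 6.0).** There are nine visits. Baseline measurements fall at Visits 2 and 3, with the clamp at Visit 3 only. Randomisation and titration run from Visit 4 to Visit 7. The measurements are repeated at Visits 8 and 9, with the second clamp at Visit 9. During treatment, "Blood pressure will be measured using the Sprint protocol with home monitors provided by us, and at weekly visits".

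**Aim 1a analyses (Section 10.0).** There are three:

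- The primary analysis is unadjusted. It compares the arms "at Visit 9 using Welch's unequal-variance an unpaired t-test to test whether the primary end point will be equal".
- Next, "in a secondary linear regression analysis we will compare DEGP in the moxonidine and amlodipine arms adjusted for these variables".
- Last comes a repeated-measures GEE of "EGP against treatment and these confounding variables at baseline and the 9 subsequent visit times", with restricted cubic splines if time acts non-linearly.

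**Covariates.** Under Aim 1a, after the degree of obesity, the list continues "baseline sympathetic activity, blood pressure, age and gender may affect EGP, these variables could confound the effect of treatment". The opening paragraph of Section 10.0 has a near-identical list: "baseline sympathetic activity and blood pressure may affect EGP these variables as well as gender and age will be included as covariates".

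**Blood pressure and treatment.** Section 7.0 expects both drugs to change blood pressure. Section 2.0 says doses are titrated so that the two arms have equivalent falls.

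**The concern.** The GEE is meant to show how treatment acts on EGP over time. That needs EGP at several visits after randomisation, and the schedule supplies one. An analyst would have to invent a replacement after the data are in, which a pre-specified plan exists to prevent.

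The same sentence can also be read as taking the covariates at follow-up visits. Blood pressure is the exposed variable: it is recorded throughout treatment, both drugs act on it, and its label in the Aim 1a list is unclear. A variable that treatment changes is not a confounder of a randomised comparison. Adjusting for it no longer estimates the total effect of treatment. The covariate question is not confined to Aim 1a, because the opening paragraph applies the list to the primary outcomes generally and Aim 3 adopts the Aim 1a approach to adjustment.

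**Working it through.** **1. Counting occasions.** The GEE needs a baseline and nine later visits, so 1 + 9 = 10 occasions. Section 6.0 provides nine visits in total. No choice of baseline visit helps:

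| Visit taken as baseline | Later visits available | Later visits needed |
|---|---|---|
| Visit 1 | 8 (Visits 2–9) | 9 |
| Visit 2 | 7 (Visits 3–9) | 9 |
| Visit 3 (first clamp) | 6 (Visits 4–9) | 9 |

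EGP requires the tracer clamp, so it exists at 2 visits, of which 1 follows randomisation. Each clamp does have several sampling points, at rest and at each insulin dose. Those describe response to insulin within a visit, not time on treatment, and the plan's sentence refers to visit times.

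**2. Splines.** Two visits identify one change per arm. Curvature in time cannot be estimated from two points, so the spline has nothing to fit. With complete data and no covariates, the treatment-by-visit term in a two-visit model is simply

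(mean at Visit 9 − mean at Visit 3, moxonidine) − (mean at Visit 9 − mean at Visit 3, amlodipine).

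**3. Sample size.** Section 10.0 derives SDs of 0.2√30 = 1.1 and 0.7√30 = 3.8, and √(1.1² + 3.8²) = 3.96, stated as 4.0. For a difference of 3 with 29 per group and two-sided alpha 0.05, the noncentral t gives 80.1% power. The stated 80% reproduces. No covariate enters it, so nothing in this point alters it.

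**4. What on-treatment blood pressure would do.** Let τ be the total effect on EGP suppression, D the between-arm difference in achieved blood pressure (positive when moxonidine is lower), and b the gain in suppression per mmHg fall. In a linear model,

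estimate adjusted for on-treatment blood pressure = τ − bD.

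τ = 3 is the plan's target. The documents give neither b nor D. The values below are assumptions chosen to show a range:

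| D (mmHg) | b = 0.1 | b = 0.2 |
|---|---|---|
| 0 | 3 − 0 = 3.0 | 3 − 0 = 3.0 |
| 5 | 3 − 0.5 = 2.5 | 3 − 1.0 = 2.0 |
| 10 | 3 − 1.0 = 2.0 | 3 − 2.0 = 1.0 |

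A simulation (29 per arm, 8,000 runs; outcome SD 4; assumed blood pressure SD 10 mmHg and baseline to on-treatment correlation 0.5) gave the same means to within 0.02. With baseline blood pressure as the covariate, the mean estimate stayed between 2.97 and 3.00 in every scenario. If amlodipine lowered blood pressure more, D would be negative and the adjusted estimate would exceed 3.

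**5. The Visit 3 response.** The covariate list omits it. Let ρ be the correlation between the Visit 3 and Visit 9 responses and σ² their common variance (an assumption). The outcome variance relevant to the comparison is σ² for Visit 9 alone, 2σ²(1 − ρ) for the change, and σ²(1 − ρ²) after adjustment for Visit 3. Since 1 − ρ² ≤ 1, and 1 − ρ² = (1 − ρ)(1 + ρ) ≤ 2(1 − ρ), adjustment is never worse than either, apart from one degree of freedom. This holds whether the endpoint is read as the Visit 9 response or as the change from Visit 3; Section 10.0 describes it both ways.

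**The case against.** The strongest reply is that on-treatment adjustment is not the natural reading. In the opening paragraph, "the degree of obesity, baseline sympathetic activity and blood pressure may affect EGP", the word baseline can cover blood pressure as well. Calling the variables confounders and listing them with age and gender suggests patient characteristics before treatment. The visit-times phrase may say only when EGP is modelled. If titration achieves equivalent blood pressure falls, D is near zero and adjustment removes nothing. All of these models are secondary.

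Most of this stands, and it reduces the blood pressure issue to a clarification. Two things remain. No passage restricts blood pressure to a value before randomisation, and equal falls are an aim rather than a guarantee: Section 6.0 provides for one dose increase, although the titration period can be extended. Also, reading the phrase as the schedule for EGP does not rescue the GEE, because that schedule does not exist.

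A reader might infer that the plan adjusts for sympathetic activity re-measured at Visit 8, the mediator at the heart of the hypothesis. The documents do not support that. Both lists specify baseline sympathetic activity, and the GEE sentence refers back to the list. A reader might also attach a large loss of power to the adjusted analyses. The documents give no share of the effect that runs through blood pressure, and the plan claims no power for those analyses.

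**Conclusion.** The Aim 1a GEE is wrong as written. It calls for ten occasions in a nine-visit trial and for EGP at visits where it is not measured. Only two occasions exist, one after randomisation, so the splines over time have no basis. This conclusion rests on the visit schedule alone.

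The timing of blood pressure is a smaller matter: the wording permits on-treatment adjustment but does not require it. The harm would depend on the difference in achieved blood pressure. It is nil at zero difference, and a 3-unit effect becomes 2.5 to 2.0 at 5 mmHg on the assumed slopes. Leaving out the Visit 3 response forgoes precision but introduces no bias. The primary Welch t-test, its sample size and its power are untouched.

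**What to change.** In Section 10.0:

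1. Replace the GEE with a model of EGP at Visits 3 and 9, with the treatment-by-visit contrast as the quantity of interest, and delete the splines over time.
2. Add the Visit 3 EGP response as a covariate in the secondary adjusted regression. It should not also be a covariate in the two-occasion model, where it is already an outcome.
3. State that blood pressure, obesity and sympathetic activity enter every adjusted model as values from Visit 2 or 3, before randomisation, and carry this through to the other aims.
4. Label any model containing on-treatment blood pressure or muscle sympathetic nerve activity (MSNA) as exploratory mediation.

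The cost is a change of wording. All the data are already scheduled; no visit, measurement or participant is added.
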